6. ANALYSIS POPULATIONS/SETS

Intention-to-Treat (ITT) Population: The principal analysis of the primary and secondary efficacy endpoints will be based on the Intention-to-Treat (ITT) population, which comprises all randomized subjects; this population will serve as the basis for all efficacy analyses. Subjects' data will be analyzed according to their randomized treatment assignment.

Modified Intention-to-Treat (mITT) Population: Comprises all subjects in the ITT population who have completed at least 42 weeks of treatment and have an evaluable post treatment histological assessment. Subjects will be analyzed according to the randomized treatment assignment.

Interim Analyses Modified Intention-to-treat (IAmITT) Population: Comprises a subset of approximately 60 subjects in the ITT population with 8% \geq MRI-PDFF at screening or at baseline with at least 1 evaluable post-Baseline MRI-PDFF value, defined as an MRI-PDFF assessment obtained at least 22 weeks after the first dose of study drug.

Safety (SAF) Population: Consists of all randomized subjects who received at least 1 dose (partial or complete) of study drug. This population will be used for all summaries of subject accountability, demographic and baseline data, and safety information, including AE incidence, clinical laboratory data, ECG data, and vital signs data. Subjects' data will be summarized according to the treatment they received. If all subjects were dosed according to randomized treatment assignment, then the safety and ITT analysis sets are identical.

PK Population: Comprises all ITT subjects with available PK measurements.

Serial PK Population: Comprises the subset of subjects who provided blood samples for evaluation of serial PK at timepoints on Day 1 and at Week 4.

7. GENERAL DATA HANDLING CONSIDERATIONS

All analyses will be conducted using SAS software Version 9.4 or higher.

All data in the database will be presented in by-subject data listings. Unless otherwise stated, all listings will be sorted by treatment group, center ID, subject number, and assessment date and time, if available.

Unless stated otherwise, continuous data will be summarized by treatment group using descriptive statistics including number of subjects (n), mean, median, standard deviation (SD), first quartile (Q1), third quartile (Q3), minimum (min) value, maximum (max) value.

Unless stated otherwise, categorical data will be summarized by treatment group using counts and percentage based on the number of non-missing values. For selected summaries, the number of missing values will be presented as a separate category with no percentage, if one or more subjects have missing data. Counts of zero will be presented without percentages.

Descriptive statistics will be presented with the following numerical precision:

- Minimum and Maximum: same as the raw data collected
- Mean, Median, Q1, and Q3: one additional decimal place to that reported for Minimum and Maximum
- SD: two additional decimal places than the Minimum and Maximum
- Percentages: reported to one decimal place if percent is <100. If the value is 100, no decimal place will be reported.

Unless otherwise noted, statistical inference will be based on two-sided testing with a 5% significance level. Confidence intervals will be at the 90% and 95% levels.

P-values will be reported to four decimal places. If the value is below 0.0001 it will be noted as < 0.0001; if the value above 0.9999 it will be noted as > 0.9999.

All data up to the time of study completion/withdrawal from the study will be included in the analysis, regardless of duration of treatment.

Numbering for data displays will be based on [International Council for Harmonization \(ICH\) E3](#) whenever possible.

7.1. Stratification and Covariates

Subjects will be randomized to achieve a 2:1 ratio of TVB-2640 50 mg to placebo, with the randomization stratified three factors: T2DM status (Yes, No), and amount of fibrosis (F2 or F3). Selected statistical models and tests will be stratified based on the randomization strata. Details on the models and tests are provided in the relevant sections below.

7.2. Evaluation of Subgroups

Select analyses for efficacy and safety endpoints will be repeated for a variety of subgroups. The subgroups are summarized in the table below. If a subject does not have a value for one of the subgroup variables they will be excluded from the subgroup. Efficacy endpoints will be analyzed by subgroup for both the ITT and mITT populations. Safety endpoints will be summarized by subgroup for the Safety population.

Endpoint	Subgroups
Co-Primary Efficacy Endpoints	

Endpoint	Subgroups

Proportion of subjects experiencing histological improvement at Week 52 in NAS (i.e., ≥ 2 points improvement in NAS with ≥ 1 point improvement in ballooning or inflammation) and without worsening of fibrosis (by NASH CRN fibrosis score)
	
 • $\geq 30\%$ reduction in MRI-PDFF from baseline to Week 52 (yes or no) – includes subjects with $\geq 8\%$ liver fat content at Baseline • $\geq 50\%$ reduction in MRI-PDFF from baseline to Week 52 (Yes or No) – includes subjects with $\geq 8\%$ liver fat content at Baseline • Stage of fibrosis at baseline (F2 or F3) • T2DM at baseline (Yes or No) • GLP-1 at baseline (Yes or No) [1] • SGLT2 at baseline (Yes or No) [2] • Statin use at baseline (Yes or No) [3] • Diabetes medication use at baseline (Yes or No) [4] • $<5\%$ reduction in weight from baseline to Week 52 (Yes or No) • Liver fat $\geq 8\%$ at baseline (Yes or No) • ≥ 17 U/L reduction in ALT from baseline to Week 52 (Yes or No) • NAS at baseline (4/5 or 6/7/8) • Race (White, Black, Asian, and other) • Hispanic (Yes or No) • Liver biopsy length ≥ 15 mm (both baseline and Week 52 biopsies) vs < 15 mm • Age categories (<40 years, 40 to <65 years, and ≥ 65 years)

Proportion of subjects experiencing both of the following at Week 52:
 
 ○ Resolution of steatohepatitis and no worsening of liver fibrosis (by NASH CRN fibrosis score). Resolution of steatohepatitis is defined as absence of fatty liver disease or isolated or simple steatosis without steatohepatitis and a NAS of 0 or 1 for inflammation, 0 for ballooning, and any value for steatosis. 
AND
	
 • $\geq 30\%$ reduction in MRI-PDFF from baseline to Week 52 (yes or no) – includes subjects with $\geq 8\%$ liver fat content at Baseline • $\geq 50\%$ reduction in MRI-PDFF from baseline to Week 52 (Yes or No) – includes subjects with $\geq 8\%$ liver fat content at Baseline • Stage of fibrosis at baseline (F2 or F3) • T2DM at baseline (Yes or No) • GLP-1 at baseline (Yes or No) [1] • SGLT2 at baseline (Yes or No) [2] • Statin use at baseline (Yes or No) [3] • Diabetes medication use at baseline (Yes or No) [4] • $<5\%$ reduction in weight from baseline to Week 52 (Yes or No) • Liver fat $\geq 8\%$ at baseline (Yes or No) • ≥ 17 U/L reduction in ALT from baseline to Week 52 (Yes or No) • NAS at baseline (4/5 or 6/7/8)

Endpoint	Subgroups

 ○ Histological improvement in NAS (≥ 2 points improvement in NAS). 	
 ● Race (White, Black, Asian, and other) ● Hispanic (Yes or No) ● Liver biopsy length ≥ 15mm (both baseline and Week 52 biopsies) vs < 15mm ● Age categories (< 40 years, 40 to < 65 years, and ≥ 65 years)
Selected Secondary Efficacy and Pharmacodynamic Endpoints	
Proportion of subjects with improvement in liver fibrosis ≥ 1 stage by NASH CRN fibrosis score without worsening of steatohepatitis (defined as no increase in NAS for ballooning, inflammation, or steatosis) at Week 52.	
 ● Stage of fibrosis at baseline (F2 or F3) ● GLP-1 at baseline (Yes or No) [1] ● SGLT2 at baseline (Yes or No) [2]
Proportion of subjects with improvement in liver fibrosis ≥ 1 stage by NASH CRN score without increase of total NAS score at Week 52.	
 ● Stage of fibrosis at baseline (F2 or F3) ● GLP-1 at baseline (Yes or No) [1] ● SGLT2 at baseline (Yes or No) [2]
Proportion of subjects with improvement in liver fibrosis ≥ 1 stage by NASH CRN score without any worsening of NASH (defined as no worsening of ballooning and lobular inflammation; a 1 grade change in steatosis may be acceptable) at Week 52.	
 ● Stage of fibrosis at baseline (F2 or F3) ● GLP-1 at baseline (Yes or No) [1] ● SGLT2 at baseline (Yes or No) [2]
Proportion of subjects experiencing both of the following at Week 52: 
 ○ Resolution of steatohepatitis on overall histopathological reading and no worsening of liver fibrosis on NASH CRN fibrosis score. Resolution of steatohepatitis is defined as absent fatty liver disease or isolated or simple steatosis without steatohepatitis and a 	
 ● Stage of fibrosis at baseline (F2 or F3) ● GLP-1 at baseline (Yes or No) [1] ● SGLT2 at baseline (Yes or No) [2]

Endpoint	Subgroups

NAS score of 0-1 for inflammation, 0 for ballooning, and any value for steatosis.
 
AND
 
o Improvement in liver fibrosis greater than or equal to one stage (NASH CRN fibrosis score) and no worsening of steatohepatitis (defined as no increase in NAS for ballooning, inflammation, or steatosis).	

Proportion of subjects experiencing both of the following at Week 52:
 
o Histological improvement at Week 52 in nonalcoholic fatty liver disease (NAFLD) activity score (NAS) (i.e., ≥ 2 points improvement in NAS with ≥ 1 point improvement in ballooning or inflammation) and without worsening of fibrosis (by NASH Clinical Research Network [CRN] fibrosis score) 
AND
 
o Improvement in liver fibrosis greater than or equal to one stage (NASH CRN fibrosis score) and no worsening of steatohepatitis (defined as no increase in NAS for ballooning,	
• Stage of fibrosis at baseline (F2 or F3)• GLP-1 at baseline (Yes or No) [1]• SGLT2 at baseline (Yes or No) [2]

Endpoint	Subgroups
inflammation, or steatosis).	
Proportion of subjects experiencing resolution of steatohepatitis and no worsening of liver fibrosis (by NASH CRN fibrosis score). Resolution of steatohepatitis is defined as absence of fatty liver disease or isolated or simple steatosis without steatohepatitis and a NAS of 0 or 1 for inflammation, 0 for ballooning, and any value for steatosis at Week 52.	
 • Stage of fibrosis at baseline (F2 or F3) • GLP-1 at baseline (Yes or No) [1] • SGLT2 at baseline (Yes or No) [2]
Proportion of subjects with histological improvement (decrease) at Week 52 in NAS by ≥ 1 point.	
 • Stage of fibrosis at baseline (F2 or F3) • GLP-1 at baseline (Yes or No) [1] • SGLT2 at baseline (Yes or No) [2]
Proportion of subjects with histological improvement (decrease) at Week 52 in NAS by ≥ 2 points.	
 • Stage of fibrosis at baseline (F2 or F3) • GLP-1 at baseline (Yes or No) [1] • SGLT2 at baseline (Yes or No) [2]
Change from Baseline in ALT, AST, and GGT at Weeks 26 and 52 and at each study visit.	
 • Stage of fibrosis at baseline (F2 or F3) • T2DM at baseline (Yes or No)
Change from Baseline in LDL-C and other lipid levels (including LDL/HDL ratio) at Weeks 26 and 52 and at each study visit.	
 • T2DM at baseline (Yes or No) • Statin use at baseline (Yes or No) [3]
Changes from Baseline in metabolic parameters, including fasting insulin, fasting glucose, HOMA-IR, adipon-IR, and HbA1c levels at Weeks 26 and 52 and at each study visit.	
 • T2DM at baseline (Yes or No)
Change from Baseline in FibroScan (Liver Stiffness Measure (kPa)) and CAP score results at Weeks 26 and 52.	
 • $\geq 30\%$ reduction in MRI-PDFF from baseline to Week 52 (yes or no) – includes subjects with $\geq 8\%$ liver fat content at Baseline • $\geq 50\%$ reduction in MRI-PDFF from baseline to Week 52 (Yes or No) – includes subjects with $\geq 8\%$ liver fat content at Baseline

Endpoint	Subgroups
Selected Exploratory Endpoints	
Change from Baseline in FAST score at Weeks 26 and 52.	
 • 30% reduction in MRI-PDFF from baseline to Week 52 (yes or no) – includes subjects with $\geq 8\%$ liver fat content at Baseline • $\geq 50\%$ reduction in MRI-PDFF from baseline to Week 52 (Yes or No) – includes subjects with $\geq 8\%$ liver fat content at Baseline
Change from Baseline in Agile 3+ score at Weeks 26 and 52.	
 • 30% reduction in MRI-PDFF from baseline to Week 52 (yes or no) – includes subjects with $\geq 8\%$ liver fat content at Baseline • $\geq 50\%$ reduction in MRI-PDFF from baseline to Week 52 (Yes or No) – includes subjects with $\geq 8\%$ liver fat content at Baseline
Change from Baseline in levels of lipidomic/metabolomic biomarkers (e.g., tripalmitin, ceramides, bile acids, diacylglycerols, and other classes of metabolites) at Weeks 4, 13, 26, and 52.	
 • On a GLP-1 at baseline (Yes or No) [1]
Selected Safety Endpoints	
Skin and subcutaneous tissue disorders TEAEs	
 • Diabetes medication use at baseline (Yes or No) [4] • COVID-19 diagnosis or COVID-19 vaccination within 30 days of skin and subcutaneous tissue disorders TEAE onset (Yes or No) • Statin use at baseline (Yes or No) [3] • GLP-1 or SGLT2 at baseline (Yes or No) [1] [2] • Female age (>50 or ≤ 50 years)
Eye disorder TEAEs	
 • Diabetes medication use at baseline (Yes or No) [4] • COVID-19 diagnosis or COVID-19 vaccination within 30 days of eye disorder TEAE onset (Yes or No) • Statin use at baseline (Yes or No) [3] • GLP-1 or SGLT2 at baseline (Yes or No) [1] [2]

[1] GLP-1 medications are identified using ATC code = 'A10BJ'

- [2] SGLT2 medications are identified using ATC code = 'A10BK'
- [3] Statin medications are identified using ATC code = 'C10AA'
- [4] Diabetes medications are identified using ATC code = 'A10' at baseline.

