4.3. Sample Size Considerations

The study is powered to test the one-sided (statistical) superiority hypothesis stipulating that a TVB-2640 50-mg dose provides better benefit than placebo based on the primary efficacy endpoint. The study estimated total sample size is approximately 162 randomized subjects (108 on TVB-2640 and 54 on placebo). The sample size was derived using the normal approximation to the binomial distribution, and the estimated power to detect a difference in the primary efficacy response of 20% (TVB-2640 40% and placebo 20% at Week 52) was at least 80% (one-sided test at the 0.05 significance level). A 2-to-1 randomization allocation was assumed (TVB-2640 to placebo), and an anticipated dropout rate of 18.5% was also applied to estimate the final total sample size (N=162).

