9. EFFICACY

9.1. Primary Efficacy Endpoint Analyses

9.1.1. Principal Analysis of the Primary Efficacy Endpoints

The principal efficacy analyses will be conducted on the ITT population. Additional sensitivity and supplementary analyses will be performed for the primary efficacy endpoints, as described in the next section.

The treatment groups will be compared based on the primary efficacy endpoints using one-sided Cochran-Mantel-Haenszel (CMH) tests stratified by the randomization stratifications T2DM status at baseline (yes or no) and amount of fibrosis at baseline (F2 or F3).

Mathematically, the null and alternative hypotheses for the primary efficacy endpoints are stated as:

$$H_0: p_T \leq p_p$$

$$H_a: p_T > p_p$$

Where, p_T is the proportion of responders in the TVB-2640 50-mg treatment group and p_p is the proportion of responders in the placebo treatment group. The higher responder proportion is a better outcome.

A Clopper-Pearson 90% and 95% CI will be derived for each treatment group, and the stratified CMH odds ratio (with its 90% and 95% CI, using the control group as a reference group) will be produced to assess the treatment effect magnitude. The difference in treatment groups response rates will be provided and also be characterized by the 90% and 95% CIs using Miettinen and Nurminen (1985).

Subgroup analyses of the primary efficacy endpoints will be performed to assess whether the treatment effect is concordant among subgroups. The planned subgroup analyses are described in Section 7.2. Analyses will be performed if there is an adequate number of subjects in each subgroup.

A subject who discontinues treatment prior to Week 42, does not provide a histological assessment on or after Week 42, or who otherwise has missing data will be considered a non-responder.

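### Four of the 16 subgroups for each co-primary endpoint are defined by change to Week 52, so their treatment contrasts are not randomised comparisons and cannot show whether the effect is concordant

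*SAP*

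**What the plan says.** SAP 7.2 gives the same 16 subgroups for each co-primary endpoint, to be analysed in both the ITT and mITT populations.

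- **Eleven are baseline variables:** fibrosis stage, T2DM, GLP-1 use, SGLT2 use, statin use, diabetes medication, liver fat of at least 8%, NAS category, race, Hispanic ethnicity and age.
- **Four depend on follow-up:** two splits on percentage "reduction in MRI-PDFF from baseline to Week 52 (yes or no"), at 30% and 50%, restricted to subjects with at least 8% liver fat at baseline; weight reduction below 5% to Week 52; and a ≥17 "U/L reduction in ALT from baseline to Week 52 (Yes or No").
- **One is mixed:** biopsy length of at least 15 mm, which needs both the baseline and the Week 52 specimen.

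SAP 9.1.1 gives the purpose: "Subgroup analyses of the primary efficacy endpoints will be performed to assess whether the treatment effect is concordant among subgroups". It points to 7.2 for the list and adds that an analysis is run only where subgroup numbers are adequate, without a threshold. Neither section marks the Week 52 change variables as descriptive or non-randomised.

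SAP 7.2 leaves out of a subgroup any subject who lacks a value for its defining variable. SAP 9.1.1 counts subjects with missing histology as non-responders in the principal analysis. Protocol 13.2.1 planned subgroups by age and race only, and SAP 11 does not mention the additions.

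**The concern.** Randomisation makes the arms comparable within strata fixed before treatment. It does not do so within strata fixed by something treatment may alter. MRI-PDFF response and ALT change are efficacy endpoints in their own right (numbers 3, 4 and 16 in SAP 7.4). Protocol 5.2 reports that the drug lowered liver fat in the earlier Phase 2a study and improved other noninvasive markers. A placebo subject who reaches a 30% fat reduction unaided is likely to differ in prognosis from a drug subject who reaches it on treatment, and the same applies to those who do not reach it.

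For fat there is a further overlap with the outcome. Steatosis is one of the three NAS components (Protocol 11.1.1, Table 3), and both co-primary endpoints require at least a 2-point NAS improvement.

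What is at stake is interpretation. A real effect could appear to vanish in these strata and be called inconsistent, or a stratum could show a difference where the drug does nothing.

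**Working it through.** **1. Planning figures.** SAP 4.3 assumes "TVB-2640 40% and placebo 20% at Week 52", a "one-sided test at the 0.05 significance level", and power that "was at least 80" percent. Allocation is 2:1 in favour of TVB-2640. On dropout the section says: "an anticipated dropout rate of 18.5% was also applied to estimate the final total sample size (N=162"). With the unpooled normal approximation:

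n(placebo) = (1.645 + 0.842)² × (0.2×0.8 + 0.4×0.6/2) / 0.2² = 43.3, rounded up to 44.

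The evaluable total is 3 × 44 = 132, and 132 / (1 − 0.185) = 162. The plan's figure is reproduced, so 40% versus 20% is a fair base for the illustrations.

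**2. An effect can be hidden.** The documents give no Week 52 marker rates by arm, so these are assumptions. Let a(T) and a(P) be the proportions reaching the marker on drug and placebo. Suppose histological response depends only on the marker: r1 with it, r0 without it, the same in both arms. Matching the planned rates requires

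r1 − r0 = 0.20 / (a(T) − a(P)) and r0 = 0.20 − a(P) × (r1 − r0).

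| a(T) / a(P) | r1 | r0 | Overall, drug vs placebo | Difference within each stratum |
|---|---|---|---|---|
| 50% / 10% | 65% | 15% | 40% vs 20% | 0 |
| 50% / 20% | 73% | 7% | 40% vs 20% | 0 |
| 60% / 20% | 60% | 10% | 40% vs 20% | 0 |
| 60% / 30% | 67% | 0% | 40% vs 20% | 0 |
| 70% / 30% | 55% | 5% | 40% vs 20% | 0 |

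Check of the third row: 0.6×0.60 + 0.4×0.10 = 0.40 and 0.2×0.60 + 0.8×0.10 = 0.20. Allocation in its marker-Yes stratum moves from 2:1 to 2 × 0.6/0.2 = 6:1.

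**3. An effect can be created.** Assume no histological effect. A prognostic factor is present in 25% of subjects, with response 50% if present and 10% if absent, so the overall rate is 0.25×0.5 + 0.75×0.1 = 20% in both arms. The drug raises the marker: 90% (factor present) and 50% (absent) on drug, 50% and 10% on placebo.

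- Marker-Yes, drug: (0.25×0.9×0.5 + 0.75×0.5×0.1) / (0.25×0.9 + 0.75×0.5) = 0.150/0.600 = 25%.
- Marker-Yes, placebo: (0.25×0.5×0.5 + 0.75×0.1×0.1) / (0.25×0.5 + 0.75×0.1) = 0.070/0.200 = 35%.
- Difference −10 points, with a true effect of 0. In marker-No it is 12.5% − 16.3% = −4 points.

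Four assumed scenarios of this type, this one included, gave −5 to −15 points in marker-Yes and −2 to −6 in marker-No. In a fifth, the drug moves the marker mainly in subjects with the factor: 95% (present) and 30% (absent) on drug, 30% and 20% on placebo. That gave +7 in marker-Yes (30.5% vs 23.3%) and −8 in marker-No (10.9% vs 19.0%). The sign depends on the assumptions.

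**4. Exclusions.** At the planned dropout, 0.185 × 162 = 30 subjects (20 drug, 10 placebo) could lack a Week 52 value and leave a subgroup labelled ITT. For ALT and weight the number may be smaller, because SAP 7.10 assigns early-termination data to a scheduled visit. For MRI-PDFF it may be larger, because Protocol 11.1.2.1 makes the scan optional in case of hardship and omits it at selected sites. The documents give no count.

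**The case against.** The strongest reply is that little rests on these tables. The principal CMH test, the success criterion and the sample size do not use them, and no decision rule or interaction test is attached. That stands, and it makes this a matter of labelling and interpretation. It does not remove the stated purpose in SAP 9.1.1, which is concordance.

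The adequate-numbers clause in SAP 9.1.1 limits the small-cell problem. It sets no threshold and does nothing about comparability.

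There is also a reason to look at weight. Protocol 9.7.1 warns that weight loss from GLP-1 agonists or SGLT2 inhibitors could confound the results, and no passage says TVB-2640 changes weight. A reader might infer that all four variables are known drug effects; the documents support that for liver fat and, as an efficacy endpoint, for ALT. Weight change remains post-randomisation and so does not give comparable arms.

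Biopsy length might be grouped with the four. It measures specimen adequacy, and nothing suggests that treatment alters it. It does condition on having a Week 52 biopsy.

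Finally, the zeros in the hiding example come from assuming that the whole effect runs through the marker. This is correct: the example shows what can happen and does not predict what will.

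**Conclusion.** The point holds for four of the 16 subgroups: the two MRI-PDFF splits, ALT change and weight change. As planned, they give non-randomised treatment contrasts that would be read as evidence for or against a consistent effect, and they omit subjects whom the principal analysis keeps as non-responders.

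The size is illustrative only. A 20-point benefit can become 0 in both strata, and a null effect can show as −15 to +7 points. All marker rates, the prognostic factor and full mediation are assumptions. That the arms lose comparability does not depend on those rates.

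Two stronger readings are not supported. A reader might infer that the primary result is biased, but the principal ITT comparison uses none of these strata. A reader might also infer that the subgroup plan as a whole is unsound, but 11 of the 16 subgroups are defined at baseline. Nor can stratum sizes be derived: the MRI-PDFF splits take only subjects with at least 8% baseline fat and a usable scan, and neither number is given.

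**What to change.** Before the SAP is finalised and the data are unblinded:

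1. Limit the concordance assessment in SAP 9.1.1 to the 11 baseline-defined subgroups.
2. Move the four Week 52 change variables to a labelled descriptive responder-association analysis: histological response by marker change within each arm, with no between-arm contrast or p-value. SAP 3.3 already has exploratory objectives relating MRI-PDFF and serum biomarkers to histology, so this has a natural place.
3. Keep biopsy length of at least 15 mm as a separately labelled specimen-adequacy sensitivity analysis, and state that it conditions on having a Week 52 biopsy.
4. List the change in SAP 11.

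This is an edit to SAP text and one table and needs no new data. N = 162 and the principal test stay as they are. The downside is that the drug-versus-placebo contrast within the four change-defined splits is no longer reported.

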13.3. Safety Analysis

Safety data will be evaluated for the Safety population (Section 13.4.2) on the basis of TEAEs, clinical laboratory assessments, vital signs, ECGs, weight, and physical examinations. Changes from Baseline in key clinical laboratory measurements, vital signs, physical examinations, and weight will be summarized by treatment group using standard descriptive statistics. A TEAE is defined as an AE that was not present prior to treatment with study drug but appeared following treatment or was present at treatment initiation but worsened during treatment. All AEs will be coded by preferred term using the Medical Dictionary for Regulatory Activities (MedDRA; current version) and NCI CTCAE (current version) grading.

TEAE incidence rates will be summarized using frequency and percentage for each treatment group and in total. TEAEs through 30 days after the last dose of study treatment will be

summarized by MedDRA (current version) system organ class and preferred term. AEs will also be summarized by NCI CTCAE grade and by causality (attribution to study treatment, related/not related to investigational medicinal product). Grades 3 and 4 AEs, SAEs, and AEs resulting in dose modification or treatment discontinuation will be summarized by preferred terms. Investigational medicinal product compliance and tolerability ratings will be summarized descriptively for each treatment group.

All safety data will be presented in data listings.

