10. SAFETY

Safety will be evaluated based on data collected for adverse events, vital signs, physical examinations, electrocardiogram (ECG), ophthalmologic examinations, and laboratory data. No formal statistical testing will be conducted for the safety analyses. Descriptive statistics will be used to evaluate safety data in this study. Summaries will be presented by treatment group.

All safety analysis reporting will be based on the Safety population. All safety data will be listed by treatment group and subject.

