An overview of TEAEs will be produced, including counts and percentages of subjects with any incidences of: TEAEs, TEAEs related to study treatment, serious adverse events (SAEs), TEAEs leading to study drug discontinuation, TEAEs with CTCAE grade 3 or higher, and fatal SAEs. The number of AEs will also be included in the summary.

In addition to the overview of TEAEs, the following summaries of AEs will be provided for the safety population by treatment group and overall:

- TEAEs by SOC and PT
- TEAEs related to study treatment by SOC and PT
- CTCAE Grade 3 or higher TEAEs by SOC and PT
- CTCAE Grade 3 or higher TEAEs related to study treatment by SOC and PT
- SAEs by SOC and PT
- TEAEs leading to treatment discontinuation by SOC and PT
- Skin and subcutaneous tissue disorders TEAEs by PT
- Eye disorder TEAEs by PT

Summaries of TEAEs by SOC, PT, and maximum severity as well as TEAEs by SOC, PT, and maximum relationship to study treatment will also be prepared.

Skin and subcutaneous tissue disorders and eye disorder TEAE summaries will also be performed for the mITT population.

A comprehensive listing of all AEs will be provided in a by-subject data listing. In addition, the following listings will be provided:

- TEAEs related to study treatment
- SAEs
- TEAEs leading to treatment discontinuation; and
- Fatal AEs.

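### Splitting skin and eye TEAEs by a COVID-19 event near their own onset leaves only affected subjects in both levels, so the table cannot compare arms on incidence

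*SAP*

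**What the plan says.** The safety rows of the subgroup table in SAP 7.2 list, for eye events, "COVID-19 diagnosis or COVID-19 vaccination within 30 days of eye disorder TEAE onset (Yes or No" and, for skin events, "COVID-19 diagnosis or COVID-19 vaccination within 30 days of skin and subcutaneous tissue disorders TEAE onset (Yes or No". The other items in those rows are diabetes medication, statin use and GLP-1 or SGLT2 use at baseline, plus female age for skin events. None of them depends on whether the event occurred.

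Four further statements determine what such a table would show:

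- SAP 7.2, population: "Safety endpoints will be summarized by subgroup for the Safety population".
- SAP 7.2, subjects who cannot be classified: "If a subject does not have a value for one of the subgroup variables they will be excluded from the subgroup".
- SAP 7, default denominator: "categorical data will be summarized by treatment group using counts and percentage based on the number of non-missing values".
- Protocol 13.3, summary measure: "TEAE incidence rates will be summarized using frequency and percentage for each treatment group and in total".

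SAP 10.1 sets the level of the parent tables, for example "Skin and subcutaneous tissue disorders TEAEs by PT". Neither document gives a reference date for subjects without the event, a separate denominator for this split, a direction for the 30-day window, or a rule for a subject with several events of which only some lie near a COVID-19 event.

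**The concern.** A subgroup summary is useful when membership is settled independently of the outcome, so that each level contains subjects with and without it. Here membership is computed from the outcome's own onset date. A subject with no skin or eye TEAE has no onset date and cannot be Yes or No. If the SAP's rule for missing subgroup values is applied, the numerator and denominator are the same people.

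Skin and eye events matter in this programme. Dry eye, skin exfoliation and palmar-plantar erythrodysesthesia were prominent in the China cohort described in Protocol 5.2. Protocol 8.3 has specific withdrawal provisions for hand-foot and visual symptoms, and SAP 10.1 gives both organ classes their own tables, repeated for mITT. A reader who sees identical percentages in both arms could take them for evidence of no difference, when they follow from the table's construction.

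The window has a separate weakness. Without a stated direction, a vaccination given up to 30 days after the event puts the subject in Yes, although it cannot have contributed to that event.

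**Working it through.** The documents give no figure for this subgroup, so there is nothing to reproduce. The check is of numerator and denominator.

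**Inputs.** Arm sizes are about 108 and 54 (SAP 4.3), used as stand-ins for the Safety population. Event rates and the share of affected subjects with a nearby COVID-19 event are not in the documents. I assumed rates of 10%, 30% and 50%, and shares of 5% and 20% with at least one such subject.

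**Formula.** Incidence in a level = subjects in the level with the TEAE / all subjects in the level.

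**Step 1: literal rule.** Let an arm have N subjects, T with the TEAE, and Y of those T near a COVID-19 event. The N − T event-free subjects have no value and are excluded. Yes is then Y/Y and No is (T − Y)/(T − Y). Both are 100% when not empty, for any N, T and Y.

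**Step 2: other denominators.**

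- Event-free subjects coded No: Yes = Y/Y; No = (T − Y)/(N − Y).
- Full arm as denominator: Yes = Y/N; No = (T − Y)/N.

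**Step 3: numbers with a large difference between arms.** Take TVB-2640 at an assumed 50% (T = 54, Y = 11) and placebo at an assumed 10% (T = 5, Y = 1), both with the 20% share, rounded to whole subjects. The arm incidences are 54/108 = 50.0% and 5/54 = 9.3%.

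| Reading | Level | TVB-2640 | Placebo |
|---|---|---|---|
| SAP 7.2 exclusion rule | Yes | 11/11 = 100% | 1/1 = 100% |
| | No | 43/43 = 100% | 4/4 = 100% |
| Event-free coded No | Yes | 11/11 = 100% | 1/1 = 100% |
| | No | 43/97 = 44.3% | 4/53 = 7.5% |
| Full-arm denominator | Yes | 11/108 = 10.2% | 1/54 = 1.9% |
| | No | 43/108 = 39.8% | 4/54 = 7.4% |

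Under the exclusion rule a difference of about 41 percentage points (50.0 − 9.3 = 40.7) disappears. Coding event-free subjects as No leaves Yes at 100%. It also makes No a mixture of event-free subjects and affected subjects with no nearby COVID-19 event; over all assumed inputs No runs from 4/53 = 7.5% to 26/53 = 49.1%. Only the full-arm denominator gives rows that add up to the arm's incidence (10.2 + 39.8 = 50.0; 1.9 + 7.4 = 9.3).

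**Step 4: preferred-term rows.** The denominator is still affected subjects only. A single term can be below 100%, but the figure is the share of affected subjects in that level who had the term, not an incidence on treatment.

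**Step 5: window.** Read in both directions, the window spans 60 days (30 + 30), and half of it lies after onset.

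**The case against.** The strongest reply is that nobody would build the table this way. The safety subgroups are said to be for the Safety population, Protocol 13.3 reports incidence by treatment group, and the non-missing denominator in SAP 7 is only a default. On that view the authors meant a breakdown of affected subjects over each arm's N. That may be the intent, but no sentence says so for this split. Naming the Safety population identifies who is being divided, and the exclusion rule in the same paragraph governs the division.

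A reader might infer that every figure in the table is 100% whatever the data. The documents do not support that. The SAP 10.1 tables are by preferred term, and those rows can be lower. A level with no subjects is 0/0, which is possible in arms of this size. The 100% belongs to the any-event row, in non-empty cells, under the exclusion rule.

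A reader might also infer that the table fails at its declared purpose of linking events to COVID-19 or vaccination. No purpose is declared. SAP 7.2 says only that selected analyses are repeated in subgroups, and a flag to help case review fits the text as well.

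On timing, a window open on both sides has some defence for a diagnosis, which can be dated after the illness began. It has much less for a vaccination.

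The small consequence also stands. SAP 10 says "No formal statistical testing will be conducted for the safety analyses". All adverse events and medications are listed by subject, and Protocol 9.7.2 requires vaccination dates, so timing can be examined by hand.

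**Conclusion.** The point holds in a limited form. Applied as written, SAP 7.2 makes the any-skin or any-eye TEAE row 100% in every non-empty Yes and No cell of both arms, and turns preferred-term rows into shares among affected subjects. Such a table cannot compare the arms on incidence. Coding event-free subjects as No does not repair the Yes level. The undirected window separately allows a vaccination after the event to count as Yes.

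The 100% result is logical and does not depend on the assumed rates, which serve only as illustration. It does rest on the exclusion rule being applied to this item, which is what the text says. The importance is minor: one descriptive safety breakdown is affected, and the main TEAE tables and the efficacy analyses are not.

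**What to change.** Remove the COVID-19 item from the subgroup table for both organ classes. For skin and for eye TEAEs separately, report by arm, with the Safety population N as denominator:

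- the number and percentage of subjects with at least one such TEAE whose onset fell within 30 days after a COVID-19 diagnosis or vaccination;
- the number and percentage of affected subjects whose TEAEs all fell outside that window.

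This wording counts subjects rather than events and settles the case of several TEAEs: one inside the window places the subject in the first row. The two rows are exclusive and add up to the arm's incidence. State the direction of the window in the definition.

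This is a descriptive breakdown that allows an arm comparison. It cannot by itself show an association with COVID-19 or vaccination, because it uses no exposure information from subjects without the event. If that question is of interest, add event rates inside and outside post-diagnosis and post-vaccination windows, with exposure defined for all subjects independently of the TEAE.

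The cost of the breakdown is a definition and a table-shell edit in the SAP. Onset dates (Protocol 12.2.3) and vaccination dates (Protocol 9.7.2) are already collected. The optional rate analysis needs somewhat more programming.
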